### 2.3. Study Design

Overview of Study Design and Key Features	

Part 1
 
Group A: Subjects with normal renal function                      Group B: Subjects with moderate renal impairment                      Group C: Subjects with severe renal impairment and subjects with ESRD not on hemodialysis
	

PK requirements to continue to Part 2  Observed Mean Values:  AUC <48 µg•hr/mL  Cmax <14 µg/mL                      (Based on emerging data, and/or data that are not expected to exceed these requirements in subjects with ESRD on hemodialysis or may require dose adjustment, subjects in Part 2 will be enrolled.)
	

Part 2 (Optional)
 
Group D: Subjects with normal renal functiona                      Group E: Subjects with mild renal impairmentb                      Group F: Subjects with ESRD on hemodialysisc
	

ESRD = end-stage renal disease; PK = pharmacokinetic
 
a If there are a sufficient number of subjects with normal renal function enrolled in Part 1 (Group A), a determination will be made regarding enrollment of matching subjects with normal renal function in Part 2 (Group D).
 
b Based on emerging data from Part 1, Group E (subjects with mild renal impairment) may not be enrolled in Part 2 if there is not a significant difference between subjects with moderate and severe impairment compared to subjects with normal renal function or if the PK can be accurately predicted.
 
c If AUC and/or Cmax is predicted to exceed the threshold, the dose may be adjusted in Group F (optional).
	

Design Features
	
 
• This will be a multi-part study, in which PK requirements must be met (observed mean values: AUC <48 µg•hr/mL and Cmax <14 µg/mL); and safety and tolerability will be reviewed before enrolling subjects into the next part of the study. In Part 1, subjects with normal renal function; subjects with moderate renal impairment; and subjects with severe renal impairment and subjects with ESRD not on hemodialysis will be enrolled. In Part 2 (optional), subjects with normal renal function, subjects with mild renal impairment, and subjects with ESRD on hemodialysis will be enrolled based on the PK, safety, tolerability, and data results of Part 1.
 
• Subjects in Groups A, B, C, D, and E will enter the clinic at Check-in (Day - 1, Period 1) before study drug administration (Day 1, Period 1). In Parts 1 and 2, on Day 1 (Period 1), subjects in Group A, B, C, D, and E will receive a single dose of study drug as follows: gepotidacin 750 mg administered as a 2-hour IV infusion. All subjects will be discharged from the clinic on Day 3 after all scheduled PK and safety assessments have been completed, and will return to the clinic for a Follow-up Visit approximately 10 days (±5 days) after dose administration. The duration of the study (from Screening to the Follow-up
 

Overview of Study Design and Key Features	
	
Visit) will be approximately 44 days.
 
 
In Part 2 (optional) of the study, subjects in Group F will participate in 2 treatment periods, with dosing in these periods separated by a washout period of at least 7 days. Subjects in Group F will enter the clinic at Check-in (Day -1, Period 1 and Day 7, Period 2) before each study drug administration (Day 1, Period 1 and Day 8, Period 2). On Day 1 (Period 1) and Day 8 (Period 2), subjects in Group F will receive a single dose of study drug as follows: gepotidacin 750 mg administered as a 2-hour IV infusion starting approximately 2 hours before the initiation of the last hemodialysis session of the week (Period 1) and gepotidacin 750 mg administered as a 2-hour IV infusion starting within 2 hours after completion of the last hemodialysis session of the week (Period 2). Subjects in Group F will be discharged from the clinic on Day 10, Period 2 after all scheduled PK and safety assessments have been completed, and will return to the clinic for a Follow-up Visit approximately 10 days (<math>\pm 5</math> days) after the last dose administration in Period 2. The duration of the study (from Screening to the Follow-up Visit) will be approximately 50 days.
 

Dosing	
 
All subjects in Group A, B, C, D, and E will receive a single dose of study drug as follows: gepotidacin 750 mg administered as a 2 hour IV infusion.
 
All subjects in Group F will receive a single dose of study drug as follows: gepotidacin 750 mg administered as a 2 hour IV infusion starting approximately 2 hours before the initiation of the last hemodialysis session of the week (Period 1) and gepotidacin 750 mg administered as a 2 hour IV infusion starting within 2 hours after completion of the last hemodialysis session of the week (Period 2).
 

Treatment Assignment	
 
Subjects will be enrolled into groups based on the classification as defined in the United States Food and Drug Administration draft guidance for industry, "Pharmacokinetics in Patients with Impaired Renal Function – Study Design, Data Analysis, and Impact on Dosing and Labeling" [DHHS, 2010]
 
Subjects with normal renal function and subjects with renal impairment will be classified based on the estimated glomerular filtration rate (eGFR; based on the Modification of Diet in Renal Disease Study). Subjects with normal renal function will also be classified based on estimated creatinine clearance (Clcr). 
 
Group A - normal renal function (eGFR <math>\geq 90</math> mL/min/1.73m^2)
 
Group B - moderate renal impairment (eGFR 30 to 59 mL/min/1.73m^2)
 
Group C - ESRD not on hemodialysis (eGFR <math>< 30</math> mL/min/1.73m^2)
 
Group D - normal renal function (eGFR <math>\geq 90</math> mL/min/1.73m^2)
 
Group E - mild renal impairment (eGFR 60 to 89 mL/min/1.73m^2)
 
Group F - ESRD on hemodialysis
 
 
 

Interim Analysis	
 
No formal interim analyses are planned for this study. However, all preliminary safety, tolerability, and available PK data will be reviewed internally at GSK after the approximate sample size has been reached in Part 1 and Part 2 (optional).
 
PK requirements must be met (observed mean values: AUC <math>< 48</math> <math>\mu\text{g}\cdot\text{hr}/\text{mL}</math> and Cmax <math>< 14</math> <math>\mu\text{g}/\text{mL}</math>) and safety and tolerability will be reviewed before enrolling subjects into Part 2 of the study
 

Overview of Study Design and Key Features	
Sample Size	
 
• The target sample size of 16 evaluable subjects with normal renal function and 8 evaluable renally impaired subjects was chosen based on feasibility, to address the objectives of the study. This sample size is considered sufficient to determine whether the pharmacokinetics in subjects with renal impairment is meaningfully different from subjects with normal renal function.
 
• The between-subject variations of PK parameters from 1000 mg 2-hour IV administration on Day 1 in the BTZ115198 study were 26.3%, 27.4%, and 27.6% for the Cmax, from AUC from time 0 to infinity (AUC(0-∞)), and AUC(0-t), respectively [see report of Study BTZ115198].
 
• For a between-subject coefficient of variation of 26.3%, 27.4%, and 27.6%, and a sample size of 16 subjects for the subjects with normal renal function and 8 subjects for the renally impaired group, it is estimated that the half width of the 90% confidence interval (CI) for the difference on log-scale will be within 21.77%, 22.75%, and 23.00% of the point estimate for Cmax, AUC(0-∞), and AUC(0-t), respectively.
 

## 2.4. Statistical Hypotheses

A formal hypothesis will not be tested; however, an estimation approach will be taken to characterize the PK of gepotidacin in subjects with mild, moderate, severe renal impairment and in subjects with ESRD (on dialysis and not on dialysis) compared with matched subjects with normal renal function.

## 3. PLANNED ANALYSES

### 3.1. Interim Analyses

No formal interim analyses are planned for this study. However, all preliminary safety, tolerability, and available PK data will be reviewed internally at GSK after the approximate sample size has been reached in Part 1 and Part 2 (optional).

### 3.2. Final Analyses

The final planned primary analyses will be performed after the completion of the following sequential steps:

1. All subjects have completed the study as defined in the protocol.
2. All required database cleaning activities have been completed and final database release and database freeze has been declared by Data Management.

## 4. ANALYSIS POPULATIONS

Population	Definition / Criteria	Analyses Evaluated
Safety	
 
Consist of all subjects who receive at least 1 dose of study drug and have at least one postdose safety assessment.
 
	
 
Study Population
 
Safety
 

PK Population	
 
Consist of all subjects who received at least 1 dose of gepotidacin and have evaluable PK data for gepotidacin.
 
	
 
PK Concentration
 

PK Parameter	
 
Consist of all subjects in the PK Population, for whom valid and evaluable PK parameters were derived. This population will be used in the assessment and characterization of PK parameters.
 
	
 
PK parameter
 
PK parameter statistical analysis
 

### NOTES :

- Please refer to [Appendix 11](#): List of Data Displays which details the population to be used for each displays being generated.

### 4.1. Protocol Deviations

- Important protocol deviations (including deviations related to study inclusion/exclusion criteria, conduct of the trial, patient management or patient assessment) will be summarised and listed.
- Protocol deviations will be tracked by the study team throughout the conduct of the study in accordance with the Protocol Deviation Management Plan.
  - Data will be reviewed prior to freezing the database to ensure all important deviations and deviations which may lead to exclusion from the analysis are captured and categorised on the protocol deviations dataset.
  - This dataset will be the basis for the summaries and listings of protocol deviations.
- A separate summary and listing of all inclusion/exclusion criteria deviations will also be provided. This summary will be based on data as recorded on the inclusion/exclusion page of the eCRF.

## 5. CONSIDERATIONS FOR DATA ANALYSES AND DATA HANDLING CONVENTIONS

Table 1 provides an overview of appendices within the RAP for outlining general considerations for data analyses and data handling conventions.

**Table 1 Overview of Appendices**

Section	Component
9.1	Appendix 1: Time & Events
9.2	Appendix 2: Treatment States and Phases
9.3	Appendix 3: Data Display Standards & Handling Conventions
9.4	Appendix 4: Derived and Transformed Data
9.5	Appendix 5: Premature Withdrawals & Handling of Missing Data
9.6	Appendix 6: Values of Potential Clinical Importance
9.7	Appendix 7: Division of Microbiology and Infectious Disease Adult Toxicity Tables for Adverse Event Assessment
9.8	Appendix 8: Multiple Comparisons & Multiplicity
9.9	Appendix 9: Model Checking and Diagnostics for Statistical Analyses.
9.10	Appendix 10: Abbreviations & Trade Marks.
9.11	Appendix 11: List of Data Displays.

## 6. STUDY POPULATION ANALYSES

### 6.1. Overview of Planned Analyses

The study population analyses will be based on the Safety population, unless otherwise specified.

[Table 2](#) provides an overview of the planned study population analyses, with full details of data displays being presented in [Appendix 11](#): List of Data Displays.

**Table 2 Overview of Planned Study Population Analyses**

Display Type	Data Displays Generated		
	Table	Figure	Listing
Subject Disposition			
Subject Disposition	Y		Y
Reason for Screening Failures	Y		Y
Reason for Withdrawals	Y		Y
Protocol Deviations	Y		Y
Inclusion and Exclusion Criteria Deviations			Y
Demography			
Demographic Characteristics	Y		Y
Study Populations	Y		Y
Renal Function			Y
Medical Conditions and Concomitant Medications			
Concomitant Medication	Y		Y
Medical Conditions (Current/Past)	Y		Y

**NOTES :**

Y = Yes display generated.

## 7. PRIMARY STATISTICAL ANALYSES

### 7.1. Pharmacokinetic Analyses

#### 7.1.1. Overview of Planned Pharmacokinetic Analyses

The pharmacokinetic (PK) analyses will be based on the Pharmacokinetic population, unless otherwise specified.

[Table 3](#) provides an overview of the planned analyses, with full details being presented in [Appendix 11](#): List of Data Displays.

**Table 3 Overview of Planned Pharmacokinetic Analyses**

Display Type	Untransformed							Log-Transformed						
	Stats Analysis			Summary		Individual		Stats Analysis			Summary		Individual	
	T	F	L	T	F	F	L	T	F	L	T	F	F	L
PK Concentrations				Y	Y  [2]	Y 	Y				Y	Y	Y	
Plasma PK Parameters	Y			Y	Y	Y	Y	Y	Y	Y	Y	Y		
Urine PK Parameters	Y			Y	Y	Y	Y	Y	Y	Y	Y	Y		
Saliva PK Parameters	Y			Y	Y	Y	Y	Y	Y	Y	Y	Y		
Dialysate PK Parameters 	Y			Y	Y	Y	Y	Y	Y	Y	Y	Y		

**NOTES :**

- T = Table, F = Figure, L = Listing, Y = Yes display generated.
- Stats Analysis = Represents TFL related to any formal statistical analyses (i.e. modelling) conducted.
- Summary = Represents TFL related to any summaries (i.e. descriptive statistics) of the observed raw data.
- Individual = Represents FL related to any displays of individual subject observed raw data.

 Linear and Semi-Log plots will be created on the same display.

 Separate mean and median plots will be generated.

 Group F subjects in Part 2 only (if needed).

#### 7.1.2. Drug Concentration Measures

Refer to [Appendix 3](#): Data Display Standards & Handling Conventions (Section 9.3.3 Reporting Process & Standards).

#### 7.1.3. Pharmacokinetic Parameters

##### 7.1.3.1. Deriving Pharmacokinetic Parameters

- Refer to [Appendix 3](#): Data Display Standards & Handling Conventions (Section 9.3.3 Reporting Process & Standards).
- The pharmacokinetic parameters will be calculated by standard non-compartmental analysis according to current working practices and using Phoenix WinNonlin Version 6.2.1 or higher.

- All calculations of non-compartmental parameters will be based on actual sampling times.
- Pharmacokinetic parameters described in [Table 4](#) will be determined from the plasma concentration-time data, as data permits.
- Pharmacokinetic parameters described in [Table 5](#) will be determined from the urine concentration data, as data permits.
- Pharmacokinetic parameters described in [Table 6](#) will be determined from the dialysate concentration data, as data permits.
- Pharmacokinetic parameters described in [Table 7](#) will be determined from the saliva concentration data, as data permits.

**Table 4 Derived Plasma Pharmacokinetic Parameters**

Parameter	Parameter Description
AUC(0-t)	Area under the concentration-time curve from time 0 (predose) to time of last quantifiable concentration, to be calculated using the linear trapezoidal rule for each incremental trapezoid and the log trapezoidal rule for each decremental trapezoid.
AUC(0-∞)	Area under the concentration-time curve from time 0 (predose) extrapolated to infinite time, calculated as: $AUC = AUC(0-t) + C(t) / \lambda z$
%AUCex	The percentage of AUC (0-∞) obtained by extrapolation (%AUCex) will be calculated as: $[AUC(0-inf) - AUC(0-t)] / AUC(0-inf) \times 100$
Cmax	Maximum observed concentration, determined directly from the concentration-time data.
Tmax	Time to first occurrence of Cmax
t 1/2	Terminal half-life will be calculated as: $t_{1/2} = \ln 2 / \lambda z$
λz	Terminal-phase rate constant
CL	Systemic clearance, calculated as: $CL = Dose / AUC(0-\infty)$
V ss	Volume of distribution at steady-state of parent drug, calculated as: $V_{ss} = MRT(0-inf) * CL$
V z	Volume of distribution of the terminal phase, calculated as: $V_z = Dose / (\lambda z * AUC(0-inf))$

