For subjects with ESRD on hemodialysis: subjects will participate in 2 treatment periods and blood and urine (if applicable) samples in Period 1 will be collected for PK analysis of gepotidacin concentrations according to the Time and Events Tables (Table 4 and Table 5). Blood and urine (if applicable) samples will be collected up to approximately 48 hours after dosing (i.e., the last sample will be collected before the next hemodialysis session). In addition, dialysate samples will be collected for the determination of gepotidacin concentrations according to the Time and Events Tables (Table 4 and Table 5).

Optional PK Assessment: with the subject’s consent, if a kidney or bladder tissue sample is collected for a nonstudy purpose during this study, excess tissue may be collected and used for the purposes of measuring tissue gepotidacin concentrations.

Figure 1 BTZ116849 Study Schematic

ESRD = end-stage renal disease; PK = pharmacokinetic

- ^a If there are a sufficient number of subjects with normal renal function enrolled in Part 1 (Group A), a determination will be made regarding enrollment of matching subjects with normal renal function in Part 2 (Group D).
- ^b Based on emerging data from Part 1, Group E (subjects with mild renal impairment) may not be enrolled in Part 2 if there is not a significant difference between subjects with moderate and severe impairment compared to subjects with normal renal function or if the PK can be accurately predicted.
- ^c If AUC and/or Cmax is predicted to exceed the threshold, the dose may be adjusted in Group F (optional).

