In Part 2 (optional) of the study, subjects in Group F will participate in 2 treatment periods, with dosing in these periods separated by a washout period of at least 7 days. Subjects in Group F will enter the clinic at Check-in (Day -1, Period 1 and Day 7, Period 2) before each study drug administration (Day 1, Period 1 and Day 8, Period 2). On Day 1 (Period 1) and Day 8 (Period 2), subjects in Group F will receive a single dose of study drug as follows: gepotidacin 750 mg administered as a 2-hour IV infusion starting approximately 2 hours before the initiation of the last hemodialysis session of the week (Period 1) and gepotidacin 750 mg administered as a 2-hour IV infusion starting within 2 hours after completion of the last hemodialysis session of the week (Period 2). Subjects in Group F will be discharged from the clinic on Day 10 of Period 2 after all scheduled PK and safety assessments have been completed, and will return to the clinic for a Follow-up Visit approximately 10 days (± 5 days) after the last dose administration in Period 2. The duration of the study (from Screening to the Follow-up Visit) will be approximately 50 days.

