### 2.2. Study Objective(s) and Endpoint(s)

Objectives	Endpoints
Primary Objectives	Primary Endpoints

 
To compare the PK of gepotidacin administered as a 750 mg IV dose in normal healthy subjects compared with subjects with mild, moderate, and severe renal impairment, and with subjects with ESRD.
 
	
 
Plasma primary PK endpoints include AUC(0-∞) and Cmax of gepotidacin, as data permit
 
Urine primary PK end points include Ae total, AUC(t0-t1), fe%, and CLr of gepotidacin, as data permit
 
Dialysate primary PK end points include AUC(t0-t1), CLD, and Frem%(0-4), of gepotidacin, as data permit
 

Secondary Objectives	Secondary Endpoints

 
To assess the safety and tolerability of gepotidacin administered as a 750-mg IV dose in normal healthy subjects compared with subjects with mild, moderate, severe renal impairment, and with subjects with ESRD
 
	
 
12-lead safety electrocardiogram readings, change from baseline in vital sign measurements (blood pressure and heart rate), monitoring of adverse events, toxicity grading of clinical laboratory test results, and physical examinations
 

 
To evaluate the secondary PK parameters of gepotidacin administered as a 750-mg IV dose in normal healthy subjects compared with subjects with mild, moderate, and severe renal impairment, and with subjects with ESRD
 
	
 
Plasma PK endpoints include AUC(0-t), CL, λz, t1/2, Tmax, Vss, and Vz, as data permit
 
Urine PK endpoint includes Ae(t1-t2) and AUC(0-t) as data permit
 
Dialysate PK endpoints include Arem(0-1), Arem(1-2), Arem(2-3), Arem(3-4), and Arem(0-4), as data permit
 

Exploratory Objectives	Exploratory Endpoints

 
To evaluate the saliva pharmacokinetics of gepotidacin (subjects in Part 1 only).
 
	
 
Primary saliva PK endpoints include AUC(0-∞) and Cmax of gepotidacin, as data permit
 
Secondary saliva PK endpoints include AUC(0-t), CL, λz, t1/2, Tmax, Vss, Vz, RAUC(0-t) and RAUC(0-∞) as data permit
 

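### SAP Table 4 has no rule for the dialysed Group F Period 1 profile: Vz is overstated by 1/(1 − Frem), and Dose/AUC(0-∞) there is not the subject's own clearance

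*SAP*

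**What the plan says.** SAP 7.1.3.1 states that the Table 4 parameters "will be determined from the plasma concentration-time data, as data permits". Table 4 then sets CL to dose over AUC(0-∞), Vz (the entry beginning "Volume of distribution of the terminal phase, calculated as") to dose over the product of λz and AUC(0-∞), and Vss by "V_{ss} = MRT(0-inf) * CL". It makes no separate provision for a profile interrupted by dialysis.

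These are named endpoints. SAP 2.2 lists, under a secondary objective that includes subjects with ESRD: "Plasma PK endpoints include AUC(0-t), CL, λz, t1/2, Tmax, Vss, and Vz, as data permit".

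Protocol 4.2 doses Group F twice. The Period 1 infusion lasts 2 hours, "starting approximately 2 hours before the initiation of the last hemodialysis session of the week (Period 1"), and the Period 2 infusion starts within 2 hours after a session ends. Inclusion criterion 5 refers to sessions of 3 to 4 hours. Protocol 4.1 says that "the last sample will be collected before the next hemodialysis session". Period 1 is therefore dialysed from about hour 2 to hour 5 or 6 and undialysed from then to about 48 hours, and Period 2 is undialysed throughout.

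SAP Table 6 derives Arem, CLD and Frem%(0-4) from the dialysate, but nothing carries them back into CL or Vz.

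**The concern.** The Table 4 formulas for CL and Vz describe the subject only if clearance is the same over the whole profile. In Period 1 dialysis clearance is switched on at about the end of infusion and off again 3 to 4 hours later. AUC(0-∞) reflects both states, while λz, fitted to the late samples, reflects only the second.

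Vz is the clear fault: an average on/off-dialysis clearance divided by an off-dialysis rate constant is not a volume of distribution. For CL the fault is one of interpretation. Dose/AUC(0-∞) then depends on session length and dialyser performance as well as on the subject.

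The stake is in the secondary comparisons. Plasma parameters are summarised by group in SAP Table 3.6, and SAP Appendix 3 gives Group F a single display label, so the SAP does not say which period supplies its value. The plasma-parameter scatter plot numbered Figure 3.6 puts all groups on one CL-versus-renal-function display. Both the protocol (9.4.1) and SAP 7.1.3.2 name CL as an example for regression on renal function. An uncorrected Period 1 value there would understate the loss of clearance in ESRD and suggest a larger terminal volume that comes from the dialysis session.

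**Working it through.** **Inputs from the documents.** Dose 750 mg over 2 h. Total clearance 43 L/h and renal clearance 16 L/h (Protocol Appendix 11), so non-renal clearance is 43 − 16 = 27 L/h. Vdss 1.30 (Appendix 11, unit not printed). Session 3–4 h, starting at about hour 2.

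**Assumptions.** Vdss is in L/kg and weight is 70 kg, so V = 1.30 × 70 = 91 L. There is no residual renal clearance. Dialysis clearance (CLD) is 3–12 L/h; neither document gives a value.

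**Check of the clearance inputs against the plan's own figures.** 750/43 = 17.44 µg·h/mL, against 17.5 simulated for normal renal function in Protocol Table 1. 750/27 = 27.8, against 28.9 for severe impairment.

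**Mass balance.** All drug leaves either by the subject's own clearance or into the dialysate:

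Dose = CL_off × AUC(0-∞) + Arem, with Arem = Frem × Dose.

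Hence Dose/AUC(0-∞) = CL_off/(1 − Frem). With λz taken after dialysis, the Table 4 Vz is (CL_off/λz)/(1 − Frem). Both carry the same factor, and this needs no assumed CLD.

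**One compartment, 27 L/h, 91 L.** The concentration at end of infusion is 6.216 µg/mL and the off-dialysis λz is 27/91 = 0.297 per h. AUC(0-2) is 6.83 µg·h/mL. For CLD 6 L/h and a 4-h session, AUC over the session is 13.12 and after it 4.91, a total of 24.86. Then:

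- Arem = 6 × 13.12 = 78.7 mg, so Frem = 78.7/750 = 10.5%
- Dose/AUC = 750/24.86 = 30.2 L/h (27 off dialysis)
- Vz = 30.2/0.297 = 102 L (91 off dialysis)
- (750 − 78.7)/24.86 = 27.0 L/h, which recovers the off-dialysis clearance

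| CLD (L/h) | 3-h session: CL and Vz | 4-h session: CL and Vz |
|---|---|---|
| 3 | +5.0% | +5.8% |
| 6 | +10.0% | +11.7% |
| 12 | +20.2% | +23.5% |

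**Two compartments.** These were matched to the severe-impairment column of Protocol Table 1 (CL 750/28.9 = 25.95 L/h, Cmax 7.93 µg/mL) with Vss 91 L and inter-compartmental clearance 3–20 L/h. The inflation runs from +4.1% (CLD 3, 3-h session) to +22% (CLD 12, 4-h session).

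**The upper end is open.** The protocol's blood flow of more than 200 mL/min is 200 × 60/1000 = 12 L/h as a floor, not a ceiling. In the one-compartment model, CLD 24 L/h gives +41% (3 h) or +47% (4 h).

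**Share of AUC in the dialysis window.** About 45–53% in the one-compartment model at 91 L, 46–55% over 50–100 kg with a 4-h session, and 31–50% in the two-compartment models.

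**Vss.** About −4% to +9% over all runs (CLD up to 24 L/h, 50–100 kg), because the shorter MRT offsets the higher Dose/AUC. In the 6 L/h, 4-h example it is +2%.

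**The case against.** The strongest reply is that a two-period design exists to show a difference between dosing before and after dialysis. On that view Period 1 Dose/AUC(0-∞) is simply the average clearance of a dialysed dose, and a higher value is a finding. That stands, so the CL part of this point is about labelling and use.

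It can also be said that the plan has safeguards. Parameters are derived as data permit, and the PK Parameter Population requires valid and evaluable parameters. Protocol 9.4.1 summarises by day and treatment, which would separate Day 1 from Day 8, and Frem% is reported alongside. These help a careful reader but set no rule. The Period 1 profile is fully sampled, so the formulas return plausible numbers and nothing flags Vz.

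The limits on importance also stand. Vz and Vss are descriptive. The ANOVA and the listed regression table (SAP Tables 3.10 and 3.11) use AUC and Cmax only, no formal hypothesis is tested, and Group F is optional, with about 4 to 8 subjects.

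A reader might go further and infer that CL, Vz and Vss in this trial will all come out 4–24% too high, or that most of the Period 1 exposure is dialysed. The documents do not support either. The percentage depends on a dialysis clearance they do not state, the share of AUC is up to about half, and Vss hardly moves.

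**Conclusion.** The point holds for Vz as written: applied to Group F Period 1, Table 4 overstates it by exactly 1/(1 − Frem), given linear kinetics and a λz fitted after dialysis. It holds for CL in a narrower sense: the ratio is valid for a dialysed dose but exceeds off-dialysis clearance by the same factor, and should not be read or plotted as the subject's systemic clearance.

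The size is unknown until Frem is measured. Roughly +4% to +24% is an illustration for an assumed 3–12 L/h, resting also on 27 L/h non-renal clearance and about 91 L, and it would be larger with a higher dialysis clearance. The off-dialysis half-life is unaffected. So are the primary AUC(0-∞) and Cmax, which do not use these formulas. This is a correction to secondary parameters of an optional group, worth making because it is cheap and the data are already planned.

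**What to change.** Add a rule to SAP Table 4 for ESRD on hemodialysis:

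- CL, Vz and Vss used in between-group summaries and in CL-versus-renal-function displays come from Period 2.
- For Period 1, Dose/AUC(0-∞) is reported only under the label *total clearance including dialysis*, and Vz is not derived uncorrected.
- Where an off-dialysis value is needed from Period 1, for example for a subject without Period 2, use CL = (Dose − Arem(0-4))/AUC(0-∞) and Vz = that CL/λz.

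Apply it to Table 3.6, the plasma-parameter Figure 3.6 and Listing 46, naming the period in each.

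The cost is one extra derivation rule and no new data. The corrected Period 1 values depend on complete dialysate recovery: drug removed but not captured would leave CL and Vz partly inflated.
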